In children with chronic pain, multiple studies have documented efficacy of CAM therapy, yet difficulties in studying pediatric CAM use have been identified and include variation in definitions of both CAM as well as lack of reporting of period of assessment, costs, insurance coverage, occurrence of adverse events, source of CAM information, and discussion of CAM use. Overall, few randomized control trials have utilized CAM therapy as an additional treatment modality versus the standard of care. Additionally, in children undergoing surgery and experiencing acute postoperative pain, little information is available regarding use of CAM therapy versus standard of care. One systematic review reported use of acupuncture did not significantly affect postoperative pain in adults experiencing arthroscopic knee surgery; however, a reduction in Ibuprofen use in postoperative pain was demonstrated in two of the studies cited. A limitation of the systematic review was that few studies have been performed in understanding the effect of CAM therapy on acute post-surgical pain. Little is known, therefore, regarding the potential effectiveness of CAM therapies as treatment modalities to decrease narcotic use in the postoperative setting. In this pilot study, our central hypothesis is that two CAM therapies, Hypnosis and Healing Touch as adjunct therapies to the standard of care, will improve analgesia use for postoperative pain. In this pilot study we will randomize 45 adolescents undergoing spinal fusion for idiopathic scoliosis to two test groups: Hypnosis with Standard of Care for Post-op Pain, Healing Touch with Standard of Care for Post-op Pain, and a control group (Standard of Care only).

AIMS:

Specific Aim One: To demonstrate the effectiveness of the addition of Hypnosis to decrease pain versus the standard of care. Hypothesis: We anticipate there will favorable changes in reported anxiety and pain scores, cortisol levels, a mean decrease in mean arterial pressure and heart rate variability and less narcotic use with the addition of Hypnosis.

Specific Aim Two: To demonstrate the effectiveness of the addition of Healing Touch to decrease pain versus the standard of care. Hypothesis: We anticipate there will favorable changes in reported anxiety and pain scores, cortisol levels, a mean decrease in mean arterial pressure and heart rate variability and less narcotic use with the addition of Healing Touch.

METHODS: (Please see attached Flow Chart for Process of the study)
Statistical Analysis: Descriptive Statistics: Standard Descriptive Statistics will be used to describe the outcomes, demographic and independent variables of interest pre- and post-intervention, overall and by intervention group. Changes in outcomes will also be calculated and descried. For continuous variables

means, medians and ranges will be produced, while frequencies and percentages will be produced for categorical variables. Means, standard deviations, medians and ranges will be computed for measured continuous variables; marginal distributions will be used for categorical factors. Graphical methods including histograms, scatterplots, and boxplots, will be used in order to understand aspects of data quantity and examine assumptions (such as normality) underlying statistical models.

Aim 1 and Aim 2: The primary outcome is decrease in reported pain and narcotic use. We will compare difference in pain pre- to post- between the two intervention and control groups, using ANOVA. Since data will be collected at multiple points pre- and post-intervention, and some randomly missing data expected, the primary analysis will employ generalized estimating equations (GEEs). The GEEs models will be adjusted for baseline characteristics, such as age, race and any important clinical characteristics. GEEs will also be used to compare the changes in reported pain and analgesic use between the three groups.

PARTICIPANTS/SAMPLE GROUP

Approximately 45 adolescents with the diagnosis of idiopathic scoliosis requiring surgery will be approaches to participate in the study. Participants will be called prior to their pre-op visit from the weekly surgical list to inquire their interest in participating. Adolescents will be female patients, ages 12-17, undergoing Posterior Spinal Fusion. Exclusion criteria include those with any other diagnosis requiring spinal fusion; adolescents with profound mental disabilities not allowing them to voluntarily assent to participate, male adolescents with diagnosis of Idiopathic Scoliosis.

Random assignation (Microsoft Excel to generate a random group assignment table) of patients to one of the following groups Randomization will be done at time of presurgical visit

- Control Group 15 female patients (Stand Pain Management)
- Healing Touch Modality 15 female patients (Standard Pain Management + Healing Touch Protocol)
- Hypnosis 15 female patients (Standard Pain Management + Hypnosis Protocol)

PARTICIPATING NEMOURS ASSOCIATES IN STUDY

Healing Touch Practitioner: Three co-investigators ([name], [name], [name]) who have successfully completed at least Level 2 of the ANCC approved curriculum Observation and Approval to be noted by the subject matter expert, the Healing Touch Certified Practitioner/Instructor and Program Coordinator of the Healing Touch Program at Nemours/AIDHC.

Certified Health Care Hypnosis Practitioner: Principal Investigator and one co-investigator are certified for Hypnosis, and will implement for this study ([name] and [name]). Each has successfully completed Hypnotherapy training and certified by the Pennsylvania Center for Hypnosis.

HEALING TOUCH GROUP

Preoperative Protocol

Day of Surgery in Pre-op Holding Area:

Patient waiting in a quiet, calm space, lights low and gentle music playing.

HT Provider offers the following HT techniques to prepare the body and energy field for the surgery.

Chakra Connection (10 min) - 30 second held positions to connect, open, and balance the energy centers to the energy field. At each location the practitioner will hold the intention to balance the flow of energy between the palms and the body area which the hands are held.

Magnetic Clearing (10 min) – Ten 30 second slow sweeps down each side of the body (total of 20 passes) to clear the energy field of any discomfort/anxiety/stress prior to surgery, creating a clean template for the procedure.

Intra-operative Protocol

HT Provider will pause at designated time on the hour to send one minute of intentional healing and decreased pain experience upon completion of procedure to the patient while in surgery.

Postoperative Protocol

Post-Op PACU Area:

HT student Provider to offer following techniques once patient is settled in bay and stable:

Open Spiral Meditation(6 min) – 30 second hand positions held at each location to open the energy field for deeper healing and to re-balance body to the field post-surgery.

Magnetic Clearing (10 min) – Ten 30 second slow sweeps down each side of the body (total of 20 passes) to clear the energy field of completed anesthesia, stress, pain.

Pain Drain (5 minutes) – A hands still polarity technique offered to "energetically drain" the discomfort from a specific area. Left hand positioned over incision site. Patient may be prone or supine during this technique.

Recovery on Inpatient Unit: Day One and Back Techniques

Within 24 hours of patient arrival to floor, the HT student Provider will provide:

Chakra Connection (10 min) - 30 second held positions to connect, open, and balance the energy centers to the energy field. At each location the practitioner will hold the intention to balance the flow of energy between the palms and the body area in which the hands are held.

Back Energy Flow Assessment and the following techniques to re-establish/and/or to increase vibrancy of energetic flow along spinal column (patient may be supine or prone for this therapy):

Lower Body Connection (4 min) - 30 second held positions, connecting lower body energy centers to the hips.

Opening Energy Flow from Neck to Sacrum (1 min) – Hands held in designated locations for one minute to establish flow along the spinal column.

Vertebral Spiral Technique (5 min) – Small rotational spirals of both hands directed on either side of the spinal column and along each vertebrae, with intention to release energetic congestion and relax the small ligaments/muscles along the spine, allowing for more effective healing, comfort and energetic flow.

Re-Assessment of Spinal Column – Should the HT student Provider find that the energy flow is still compromised, then the above Vertebral Spiral Technique will be performed again and reassessment will follow. Should assessment indicate the energy flow is still impeded, the HT student provider will encourage flow with the Hands Still technique for 2 minutes. (Palm of one hand placed at the base of the neck and the other palm at the sacral area, with the intention held to open the flow of energy and to re-establish the spinal energy connection.)

Energetic Sweep down Spinal Column (1 min) - Completes back techniques with gentle brushing motions down the back to the waist. Random patterning from neck to waist.

Daily on Inpatient Unit (after above noted Back Techniques post op Day One:

Assessment of Spinal Energy Flow, energy centers flow, and pain level(s) to be determined by the HT Provider. Protocol for findings are as follows:

If pain is noted by patient, Pain Drain to be offered. (see Post-op PACU area), followed by Magnetic Clearing.

Magnetic Clearing (10 min) – Ten 30 second slow sweeps down each side of the body (total of 20 passes) to clear the energy field of completed narcotics, stress, pain.

If energy centers are found to be compromised, (but the spinal energy flow is open), then a Chakra Connection will be offered.

Chakra Connection (10 min) - 30 second held positions to connect, open, and balance the energy centers to the energy field. At each location the practitioner will hold the intention to balance the flow of energy between the palms and the body area in which the hands are held.

If spinal energy flow is found to be compromised, Back Techniques to be offered.(see Inpatient Unit Day One protocol)

(This continues as a daily offering until patient is discharged from the hospital.)

HYPNOSIS GROUP

Preoperative Protocol

Day of Surgery in Pre-op Holding Area

Prior to preoperative dose of midazolam and gabapentin Hypnosis practitioner will provide Wakeful hypnosis using a standardized script of suggestions (15 minutes) to achieve a state of focused attention with heightened receptivity for acceptable suggestions targeting relaxation, comfort and healing.

Intra-operative Protocol

Patient will listen to the tape recorded voice of the preoperative hypnosis practitioner using a standardized script of suggestions during anesthesia encouraging:

- increased feelings of relaxation
- · increased feelings of security
- minimal discomfort
- decrease in nauseas and vomiting
- return to normal appetite
- · increase in physical endurance
- quick recovery
- total body wellness

Postoperative Protocol

The same hypnosis practitioner will provide Wakeful hypnosis using standardized script of suggestions during the wake-up period in the Post-Anesthesia Care Unit (PACU) suggesting:

continued physical healing

- decrease in side effects
- quick recovery

Patient will be seen daily by the same hypnosis practitioner until discharge to provide Wakeful hypnosis using standardized script of suggestions to continue to achieve continued healing and recovery.

A Randomized Controlled Trial Piloting the Effectiveness of Complementary Therapies to Reduce Pain (decrease morphine use) in Spinal Fusion Patients

Purpose of Study: To describe the effectiveness of complementary alternative therapies in improving pain outcomes in patients undergoing spinal fusion. Hypothesis One: We propose that CAM therapies will decrease pain in this pediatric population by decreased morphine usage, stable VS, less anxiety compared to the standard of care.

SAMPLE: Ages 12-17 years, N = 45, (15 in each group)

Cortisol level, opioid requirement

AFTER CONSENT/ASSENT MEASUREMENTS OBTAINED: Anxiety Scale, Pain Scale, Blood Pressure, Heart Rate, Temperature, CBC, Cortisol level.

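### The pain analysis allows, but does not commit to, adjustment for the pain score already listed before randomisation; and a change in analgesic use has no stated reference point or window

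*Combined protocol and SAP*

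**What the plan says.** Under Statistical Analysis, Aim 1 and Aim 2, the primary outcome covers both pain and narcotic use. For pain the plan says "We will compare difference in pain pre- to post- between the two intervention and control groups, using ANOVA". It then makes GEE the primary analysis, giving as the reason "Since data will be collected at multiple points pre- and post-intervention, and some randomly missing data expected". On covariates it says "The GEEs models will be adjusted for baseline characteristics, such as age, race and any important clinical characteristics". It closes with "GEEs will also be used to compare the changes in reported pain and analgesic use between the three groups".

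On timing, Participants/Sample Group says "Randomization will be done at time of presurgical visit". The flow chart lists a pain scale among the measurements after consent and assent, above the RANDOMIZE step. The Pre-Op row below that step lists a pain scale again. Pain is then listed at PACU, on post-operative days 0-4 and at 4 weeks.

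Opioid requirement appears at PACU, on days 0-4 and at 4 weeks. It is in neither the after-consent list nor the Pre-Op row. The hypotheses concern differences from standard of care: Specific Aim One expects "less narcotic use with the addition of Hypnosis", and the flow chart's Hypothesis One expects "decreased morphine usage, stable VS, less anxiety compared to the standard of care".

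**The concern.** **Pain.** Subtracting the pre score fixes its coefficient at 1. Adjusting for it lets the data choose the coefficient. When pre and post scores are weakly correlated and similarly variable, subtraction adds noise, and with 15 patients per arm there is little precision to spare. The covariate sentence would let an analyst include baseline pain, but it names only age and race. The GEE form is also open: the pre scores could be responses, covariates, or part of a change. Two analysts following the text could fit primary models of different precision. Which score counts as pre is not stated either.

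**Opioids (wording only).** A change needs a starting value. The first opioid value listed is at PACU, after both intervention arms have had pre- and intra-operative therapy. A change from PACU would therefore not be a change from an untreated state, and it would not match the between-arm hypotheses. The window is not stated.

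**Working it through.** **Inputs from the documents.** N = 3 × 15 = 45, with g = 3 arms. No SD, correlation, effect size or power is given, so there is no design calculation to reproduce.

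**Assumed inputs.** k = pre-score SD / post-score SD, from 0.25 to 1. ρ = pre-post correlation, from 0.1 to 0.7. Complete data, one post score, no other covariates.

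**Formula.** In units of the post-score variance:

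- change score: 1 + k² − 2ρk
- baseline-adjusted: (1 − ρ²) × [1 + 1/(N − g − 2)] = (1 − ρ²) × (1 + 1/40) = (1 − ρ²) × 1.025

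Ratio (change / adjusted) = (1 + k² − 2ρk) / [(1 − ρ²) × 1.025].

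Since 1 + k² − 2ρk = (1 − ρ²) + (k − ρ)², the ratio cannot fall below 1/1.025 = 0.976, reached when k = ρ.

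- k = 1, ρ = 0.1: 1.80 / 0.99 / 1.025 = 1.77
- k = 1, ρ = 0.2: 1.60 / 0.96 / 1.025 = 1.63
- k = 0.5, ρ = 0.5: 0.75 / 0.75 / 1.025 = 0.98

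| k | ρ=0.1 | 0.2 | 0.3 | 0.5 | 0.7 |
|---|---|---|---|---|---|
| 1 | 1.77 | 1.63 | 1.50 | 1.30 | 1.15 |
| 0.75 | 1.39 | 1.28 | 1.19 | 1.06 | 0.98 |
| 0.5 | 1.13 | 1.07 | 1.02 | 0.98 | 1.05 |
| 0.25 | 1.00 | 0.98 | 0.98 | 1.06 | 1.36 |

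Simulation of 60,000 trials of 3 × 15 agrees: 1.77 (k=1, ρ=0.1), 1.61 (1, 0.2), 0.98 (0.5, 0.5) and 0.98 (0.25, 0.2).

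In patients, 15 per arm on change scores is worth 15/1.63 = 9.2 per arm adjusted at k=1, ρ=0.2. It is worth 15/1.28 = 11.7 at k=0.75, ρ=0.2, and 15/0.976 = 15.4 where adjustment loses.

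**Several post scores.** For the mean of six (PACU and days 0-4) with correlation w between them, the variance of the mean is (1 + 5w)/6. At w = 0.5 this is 0.583, so k and ρ are each divided by √0.583 = 0.764. With ρ = 0.2 the ratio is 2.12 at k=1, 1.14 at k=0.5 and 0.98 at k=0.25. The pattern is the same: possibly large, possibly nil.

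**What the GEE form does.** With complete data, entering the pre score as a response with free arm-by-time terms reproduces the change-score estimate. With missing data this need not hold: in one check with 6 of 45 post scores missing and exchangeable correlation, the GEE gave 0.297 and the complete-case change score 0.358. Constraining the baseline arm means to be equal gave these simulated variances relative to baseline adjustment (exchangeable working correlation, one post score, 2,500 trials each):

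| k, ρ | constrained baseline | change score, same trials |
|---|---|---|
| 1, 0.2 | 1.00 | 1.65 |
| 0.5, 0.2 | 1.00 | 1.07 |
| 0.5, 0.5 | 1.07 | 0.97 |
| 0.25, 0.5 | 1.21 | 1.05 |

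The constraint recovers the precision in the first two rows but not in the last two. The plan does not say whether it applies.

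**Opioids.** No arithmetic applies. A stray flow-chart line above the after-consent list reads "Cortisol level, opioid requirement". The Hypnosis 4-week cell breaks off after the anxiety scale, and the other two arms' cells continue with cortisol and opioid requirement. The line is therefore probably the displaced end of that cell and not a baseline opioid measurement.

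**The case against.** The strongest reply is that the large ratios use the wrong comparator. The primary analysis is a GEE that is already adjusted, and its covariate wording is open-ended. Baseline pain is an obvious clinical characteristic in a pain trial. If it is included, nothing is lost; if baseline arm means are constrained equal, much of the loss can disappear. The large figures need the covariate left out, no such constraint, and k near 1. This stands as a limit on the size. It does not remove the point, because the text commits to none of these choices and the ANOVA it describes is an unadjusted comparison of differences.

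It also stands that this is a 45-patient pilot, that no bias or contradiction is shown, and that the position of the after-consent score before allocation rests on flow-chart order alone. The Pre-Op entry may be a second measurement or the same set listed twice.

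On opioids, a reader might infer that analgesic use has no stated comparison at all. The documents do not support that: the comparison is between the three groups, and the hypotheses give its direction. The word changes may even govern only reported pain. What is missing is the reference point and the window.

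**Conclusion.** The point holds as one of precision and wording. The plan permits adjustment for baseline pain without committing to it, although a suitable score is already listed. For one post score with complete data, the change-score variance is 0.98 to 1.77 times the adjusted variance over the assumed ranges. The documents do not show where in that range this trial lies. The case for acting is the asymmetry: at worst about 2% lost, against a possibly substantial gain.

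A reader might infer that the change-score analysis is biased, or that the plan ignores baseline pain. Neither follows: under randomisation the change score is unbiased, and it uses the pre score. Nor do the documents show that the trial will lose the equivalent of several patients per arm; that needs particular values of k and ρ and particular unstated model choices.

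For opioids, the defect is confined to the missing reference point and window. No passage makes PACU the reference, and no numerical effect is claimed.

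**What to change.** **Pain.**

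- In the primary GEE, use post-operative pain scores as the response and name the after-consent pain score as a covariate.
- Use the same covariate in place of the unadjusted ANOVA of differences. Changes can still be described; a model of change with this covariate gives the identical treatment estimate.
- Confirm that the after-consent score is taken before allocation, and say whether the Pre-Op entry is the same measurement or a separate one.
- Say which post-operative times enter the contrast, and keep the 4-week score separate.

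**Opioids.** State that post-operative opioid use is compared between arms over a named window, with no change from the PACU value. A more elaborate opioid model, such as rates per hour weighted by interval length, is not needed to correct this wording and would require interval times that the documents do not list.

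**Cost.** Analysis wording only, with no new measurements or visits. The covariate uses one degree of freedom, a factor of 1.025 in variance.
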